4.2 Env (A, B, C, A/E) / Gag (C) DNA plasmids

The polyvalent DNA vaccine contains equal amounts of 5 individual DNA plasmid components utilizing the same vector pSW3891 (45): 4 plasmids each containing a codon optimized gp120 gene sequence from 3 primary HIV-1 subtype A, B, C envelope proteins and a CRF01_AE consensus, and a fifth plasmid containing a codon optimized *gag* gene from subtype C ([Table 4-1](#)).

DNA vaccines

The 4 gp120-expressing (Env-A, B, C and A/E) and one Gag expressing (Gag-C) plasmids were constructed with the vector pSW3891 backbone. This backbone contains the following elements: 1) human cytomegalovirus (CMV) immediate-early promoter/Intron A enhancer for high-level gene expression in a wide range of mammalian cells; 2) the bovine growth hormone (BGH) polyadenylation signal for proper termination and processing of the recombinant transcript; 3) the tissue plasminogen activator (tPA) signal peptide sequence to lead the secretion of encoded proteins; 4) pUC origin for high copy replication and maintenance of the plasmid in *E. coli*; and 5) Kanamycin (Kan) resistance gene for selection in *E. coli*. The gp120 and *gag* cDNA that were cloned into the pSW3891 vector are described in [Table 4-1](#). The codon optimized gp120 and *gag* cDNA genes were chemically synthesized at Geneart (Germany). Each codon optimized gp120 gene was individually cloned into NheI and BamHI sites in frame with tPA leader sequence of the pSW3891 vector. The *gag*-C gene was cloned into HindIII and BamHI sites of the pSW3891 vector.

Table 4-1 Five plasmids each encoding a codon optimized pg120 or gag gene sequence

DNA Vaccine Name	Vector Backbone	gp120 or gag Gene Insert	HIV-1 Isolate	GenBank Accession No. of original viral gene	Size (bp)
PDPHV-ENV-A	pSW3891	gp120-A2-opt	92UG037.1	U09127	6163
PDPHV-ENV-B	pSW3891	gp120-JR-FL-opt	JR-FL	U63632	6181
PDPHV-ENV-C	pSW3891	gp120-C2-opt	93MW965.26	U08455	6151
PDPHV-ENV-E	pSW3891	gp120-AE-Cons-opt	Subtype A/E consensus	N/A	6163
PDPHV-GAG-C	pSW3891	gag-C8-opt	96BW15C02	Af110974	6166

The DNA vaccines were manufactured at Waisman Biomanufacturing (Madison, WI) under GMP-compliant conditions.

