
6.4.4.3 Primary analyses of neutralization magnitude-breadth curves

Separate analyses of magnitude-breadth of neutralization will be conducted for the Tier 1B isolate panel and for the Tier 2 isolate panel, for all analyses whether primary, secondary, or exploratory.

For each panel, individual magnitude-breadth curves will be plotted by vaccine arm and pooled placebo, with average magnitude-breadth curves overlaid on the plots. For each panel, the area-under-the-magnitude-breadth curve (AUC-MB) (61) will be computed for each participant, as described in (62). Dunnett’s procedure will be applied with 2-sided alpha = 0.05 to determine which of the two vaccine arms have a significantly higher mean AUC-MB than that of the pooled

placebo groups, as described in (63) (see their formula (1.1)). This procedure will be applied to construct 95% CIs about the 2 differences in mean AUC-MB for each vaccine regimen versus the pooled placebos (vaccine – placebo), which simultaneously have at least 95% coverage probability.

The vaccine regimens will be ranked by the estimated mean of the AUC-MB curves. The vaccine regimen with the highest estimated mean will be selected as the best regimen.

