10.5.2 Neutralizing antibody assay (Part B)

HIV-1-specific nAb assays will be performed on serum samples from study participants taken at the primary immunogenicity timepoint(s). Specimens from the baseline and other timepoints may also be analyzed at the discretion of the HVTN Laboratory Program, which may be contingent on the results of the primary immunogenicity timepoints. The TZM-bl assay will test neutralization of the vaccine strains and at least one highly neutralization-sensitive tier 1A virus. The global panel and/or clade-specific panels may be used to assess tier 2 virus neutralization (61, 66). Additional TZM-bl assays may be performed to test neutralization of Tier 1B strains.

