The following table lists the antigens for exploratory analysis if sufficient immunogenicity responses are observed (for Part B only).

Panel	Antigen	Clade	Isolate
Extended Clade C gp120 Panel	1394C9_G1.D11gp120.avi	C	IgG
	1428_D11gp120.avi/293F	C	IgG
	1641A7_D11gp120.avi/293F	C	IgG
	CAP210_D11gp120.avi/293F	C	IgG
	CAP45_D11gp120.avi/293F	C	IgG
	Ce0042_D11gp120.avi/293F	C	IgG
	CH505TF_D7gp120.avi/293F	C	IgG
	Du156_D11gp120.avi/293F	C	IgG
	96XM651.D11gp120.avi	C	IgG
	TV1c8_D11gp120.avi/293F	C	IgG
Extended Clade C V1V2 Panel	gp70-CAP45.2.00.G3 V1V2	C	IgG
	gp70-1294C9G1_V1V2	C	IgG
	gp70-1012.11.TC21.3257 V1V2	C	IgG
	gp70-1051.12.C22 V1V2	C	IgG
	gp70-Ce1176 V1V2	C	IgG
	gp70-Ce704010042_2ES V1V2	C	IgG
	gp70-ConcC V1V2	C	IgG
	gp70-DU156.12.V1V2	C	IgG

Several criteria are used to determine if data from an assay are acceptable and can be statistically analyzed. The blood draw date must be within the allowable visit window as determined by the protocol. Second, if the blank bead negative control exceeds 5,000 MFI, the sample will be repeated. If the repeat value exceeds 5,000 MFI, the sample will be excluded from analysis due to high background.

Samples from post-enrollment visits are declared to have a positive response if they meet three conditions:

1. The net MFI values \geq antigen-specific cutoff (based on the 95th percentile of the baseline net MFI values that are greater than/equal to 100 but less than 6,500). If the cutoff is greater than 5,000 net MFI, then the antigen will be excluded from analysis.
2. The net MFI values are greater than 3 times the baseline net MFI values.
3. The MFI values are greater than 3 times the baseline MFI values.

For each of gp120 breadth panel and gp70 V1V2 breadth panel, magnitude-breadth (MB) and AUC-MB will be calculated for each participant by isotype and post-vaccination timepoint.

Contingent upon these results, samples may be titrated to calculate antibody titers (EC50/AUC), in which case geometric mean titers will be compared.

The treatment arm of receiving 2 protein/GLA-SE vaccines is labelled as T1, the treatment arm of receiving 3 DNA prime vaccinations and 2 DNA+Protein/GLA-SE boost vaccinations in Group 2 is labelled as T2, and the treatment arm of receiving 5 DNA+Protein/GLA-SE vaccinations in Group 3 is labelled as T3. The placebo arm in Part A is labelled as P_A. The placebos in Groups 2 and 3 in Part B are pooled and the treatment arm is labelled as P.

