10.2 Neutralizing antibody (NAb)

Neutralizing antibodies (NAb) against tier 1A, tier 1B and tier 2 strains of HIV-1 will be measured in TZM-bl cells as a function of reductions in Tat-induced luciferase (Luc) reporter gene expression after a single round of infection with molecularly cloned, Env-pseudotyped viruses. TZM-bl (also called JC57BL-13) is a Hela cell clone that was engineered to express CD4 and CCR5 and to contain integrated reporter genes for firefly luciferase and *E. coli* β -galactosidase under control of an HIV-1 long terminal repeat (LTR). The cells are highly permissive to infection by most strains of HIV, including primary HIV-1 isolates and molecularly cloned Env-pseudotyped viruses. DEAE-dextran is used in the medium during neutralization assays to enhance infectivity. Expression of the reporter genes is induced in trans by viral Tat protein soon after infection. Luciferase activity is quantified by luminescence and is directly proportional to the number of infectious virus particles present in the initial inoculum. The assay is performed in 96-well culture plates for high throughput capacity. Use of a clonal cell population provides enhanced precision and uniformity. The assay has been formally optimized and validated for single-round infection with either uncloned or molecularly cloned Env-pseudotyped viruses produced by transfection in 293T cells.

Assays will be performed using cryopreserved serum sample starting at a specific dilution determined by the lab PI. Titers will be defined as the serum dilution that reduced relative luminescence units (RLU) by 50% and 80% relative to the RLU in the virus control wells after subtraction of background RLU in control wells (ID50 and ID80). Neutralization ID50 and ID80 titers will be measured against MW965.26 (tier 1A vaccine strain), the tier 2 vaccine strains JR-FL and 92UG037.1, and the heterologous tier 1B strains Bx08.16, Q23.17, 6525.3, ZM197M-PB7, and 1056-10.TA11.1826. The global panel and/or clade-specific panels may be used to assess tier 2 neutralization on a selected subset of participants.

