A response is considered positive if the neutralization titer is above a pre-specified cutoff. Magnitude of response will be measured by the natural log of the ID50 and ID80 titer. An aggregate measure of response will be calculated as the area-under-the-magnitude-breadth curve (AUC-MB), which is equivalent to the mean log titer across all viruses in tier 1B and tier 2. If a titer is left censored, half the left censor limit will be used as the titer value.

Neutralization titers will be measured on the primary immunogenicity samples at visit 22 (at week 34, 2 weeks post the 5th vaccination) from all 48 Part B participants. Specimens from other time points may also be analyzed at the discretion of the HVTN Laboratory Program, which may be contingent on the results of the primary immunogenicity time point. Those time points may include week 0 (visit 12 - baseline), week 14 (visit 17 – 2 weeks post 3rd vaccination), week 26

(visit 18 – 2 weeks post 4th vaccination), and/or week 61 (visit 24 – 6 months post 5th vaccination).

Positive response rates will be compared between treatment groups within each time point using Barnard exact test. Titers and AUC-MBs will be compared between treatment groups within each time point using Wilcoxon rank sum test. Positive response rates, titers, and AUC-MBs between time points within treatment group will be also compared using McNemar's tests and Wilcoxon signed rank test, respectively, if neutralizations will be measured at multiple time points.

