10.3 Antibody-Dependent Cell-Mediated Cytotoxicity (ADCC)

The GranToxiLux ADCC (GTL-ADCC) assay will be used to test reactivity against HIV-env protein coated cells (% Granzyme readout). Cells coated with either gp120 protein A, gp120 protein B, gp120 protein AE, or Clade C TV1 gp120 individually will be tested in a 96 well plate for the Grantoxilux (GTL assay). Participant sera in addition to control sera will be incubated with these HIV proteins and ADCC detected through the use of a Granzyme B substrate (GTL).

Cells infected with HIV-1 IMC TV1, WITO and CM235, individually, will be tested in a 96 well plate for the Luciferase ADCC assay. Participants sera in addition to controls were incubated with the IMC-infected cells and ADCC detected through the use of Vivirene luminescence.

The following evaluation criteria will be employed for this assay:

- i) GTL: The data from the assay is quantitative. The frequency of positive responses (% responders) peak ADCC, and area under the curve (AUC) will be tabulated to assess differences in ADCC response between the treatment groups.
- ii) Luciferase: The data from the assay is semiquantitative. The frequency of positive responses (% responders) peak of specific killing and AUC will be tabulated and compared between the treatment groups.

Positivity criteria are as follows:

- i) GTL: peak % response $\geq 8\%$

- ii) Luciferase: peak % response $\geq 10\%$, after background subtraction of baseline response and positivity at one of the first two dilutions.

The sera samples at v12 (day 0) and v22 (day 238) from the 48 participants in Part B will be assayed for ADCC responses. Based on the responses at v22, assays may be performed on these participants samples at v17 (day 98), v19 (day 182), and v24 (day 425).

Positive response rates will be compared between treatment groups within each time point using Barnard exact test. Peak of ADCC and AUC ADCC will be compared between treatment groups within each time point using Wilcoxon rank sum test. Positive response rates, peak ADCC, and AUC ADCC between time points within treatment group will be also compared using McNemar's tests and Wilcoxon signed rank test, respectively, if neutralizations will be measured at multiple time points.

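### The SAP's pooled neutralization AUC-MB averages two vaccine-insert viruses with five heterologous ones and drops the Protocol's split by tier

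*Protocol*

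**What the plan says.** Protocol 10.5.2 commits to testing the vaccine strains: "The TZM-bl assay will test neutralization of the vaccine strains and at least one highly neutralization-sensitive tier 1A virus". It then says that global or clade-specific panels may be used for tier 2, and that tier 1B assays may be added.

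SAP 10.2 fixes the list. It names MW965.26 as a tier 1A vaccine strain, followed by "the tier 2 vaccine strains JR-FL and 92UG037.1, and the heterologous tier 1B strains Bx08.16, Q23.17, 6525.3, ZM197M-PB7, and 1056-10.TA11.1826". The global and clade-specific tier 2 panels stay optional, and only for a selected subset of participants.

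Protocol Table 4-1 confirms the match. The subtype B plasmid carries "gp120-JR-FL-opt", and the subtype A plasmid is built from isolate 92UG037.1. Protocol 4.3.1 says that the gp120 proteins match the Env genes in the DNA.

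SAP 10.2 then defines AUC-MB as an aggregate "which is equivalent to the mean log titer across all viruses in tier 1B and tier 2" and compares it between groups by Wilcoxon rank sum test. SAP 10.2.1 lists one AUC-MB comparison per visit, not split by tier.

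Protocol 6.4.4.3 differs. It requires Tier 1B and Tier 2 to be analyzed separately at every level of analysis, and for those scores it says: "The vaccine regimen with the highest estimated mean will be selected as the best regimen".

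For binding antibody, SAP 10.1 lists the vaccine proteins as their own panel and restricts the breadth score: "For each of gp120 breadth panel and gp70 V1V2 breadth panel, magnitude-breadth (MB) and AUC-MB will be calculated for each participant".

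**The concern.** Protocol 4.1 sets the aim as cross-reactive antibody against diverse viruses, and Protocol 4.4 says that the secondary immunogenicity results will rank the regimens and inform further development. A magnitude-breadth score serves that aim to the extent that it reflects viruses outside the vaccine.

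The SAP's pooled score mixes the two kinds of virus, and no passage removes the matched ones. T3 receives protein five times and T2 twice (Protocol 8.1), so a titer gain confined to the insert strains is possible. It would appear in the pooled score just as a broader response would. The two documents also define the same score differently, so whoever programs it must choose between them.

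**Working it through.** **Counts** (SAP 10.2 list, checked against Table 4-1)

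- Tier 1B: 5 viruses, all labelled heterologous.
- Tier 2: 2 viruses, both vaccine inserts.
- MW965.26 is tier 1A, so it falls outside the score.
- Matched share of the SAP pooled score: 2/(5 + 2) = 28.6%.
- Matched share under the Protocol split: Tier 1B 0/5 = 0%; Tier 2 2/2 = 100% if the optional panel is not run.
- If k heterologous tier 2 viruses were run for everyone, the pooled share would be 2/(7 + k): 16.7% for k = 5, 11.8% for k = 10, 7.4% for k = 20. The documents give no k.

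**Shift in the score when all titers are detectable**

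The score is a mean of log titers, so a gain by a factor F on the matched strains alone multiplies the geometric-mean score by F^(2/7).

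- F = 3: 3^(2/7) = 1.37, or 2 × ln 3/7 = 0.31 natural-log units.
- F = 10: 10^(2/7) = 1.93, or 2 × ln 10/7 = 0.66.

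If one arm leads by m (log scale) on the matched strains and trails by h on the heterologous ones, the pooled difference is (2m − 5h)/7. It favors that arm whenever m > 2.5h. A 3-fold matched lead therefore outweighs a heterologous deficit of up to 3^(1/2.5) = 1.55-fold.

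**Effect of censoring**

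SAP 10.2 sets a left-censored titer to half the limit. Matched titers that are censored in both arms add the same constant to each, so the shift shrinks toward zero as censoring rises.

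**Chance of a difference between arms**

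The plan's evaluable number is reproduced first: 21 × 0.85 = 17.85, so 18 per arm (Protocol 6.1.2). The documents give no SDs or response rates, so these are assumed: normal natural-log titers, between-person SD 0.5 to 1.0, within-person virus SD 0.7 to 1.0. For the censored rows the limit is 1:10, the tier 1B median 1:40, and 2 to 10% of matched titers are detectable in the comparator arm. One arm is shifted on JR-FL and 92UG037.1 only. The test is two-sided Wilcoxon at 0.05.

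| Score | Matched-only gain | Shifted arm has higher mean | p ≤ 0.05 |
|---|---|---|---|
| Pooled, all detectable | 3-fold | 80–95% | 13–34% |
| Pooled, all detectable | 10-fold | 97–100% | 39–91% |
| Pooled, matched mostly censored | 3-fold | 56–83% | 5–15% |
| Pooled, matched mostly censored | 10-fold | 71–100% | 6–75% |
| Five heterologous strains | any | about 50% | about 5% |

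A separate run used SD units, between-virus correlation 0.2 to 0.8 and no censoring. A 1 SD matched-only shift gave p ≤ 0.05 in 14 to 30% of trials on the pooled score and 84 to 96% on a Tier 2 score made of the two insert strains.

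**The case against.** The case on the other side is substantial.

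- A reader might infer that the trial will select the wrong regimen as best on the pooled score. The documents do not support this. The selection rule is in Protocol 6.4.4.3 and applies to tier-split scores. The SAP has no selection rule and only tests its pooled score. Under the Protocol, the Tier 1B score contains no vaccine strain.
- A reader might infer that Protocol 10.5.2 itself puts vaccine strains into a breadth score. It says only that they are tested.
- A Tier 2 score made wholly of insert strains is conditional. It combines the Protocol's split with the SAP's list and assumes that the optional panel is not run. The Protocol's Tier 2 panel can reasonably be read as the global or clade-specific reference panels.
- The documents speak of a best regimen, not a broader one. Protocol 6.4.4.4 reads the score as an average log titer over the test panel, so it was never pure breadth.
- SAP 10.2.1 tabulates response rates and titers by isolate, so a matched-only pattern would be visible. This mitigation is real, but the aggregate comparison does not use those tables.
- Tier 2 titers may be mostly undetectable. Protocol 4.4.1 expects less frequent tier 2 responses, and Protocol 4.8.1 reports that most sera from the first-generation trial inhibited standard tier 2 panels (not the insert strains) by less than 50% at 1:10. The censored rows show that the effect can then be close to nil.
- Nothing in the documents shows that a gain would be confined to the matched strains. Five protein doses could raise tier 1B titers too.
- For ADCC, SAP 10.3 says "Cells coated with either gp120 protein A, gp120 protein B, gp120 protein AE, or Clade C TV1 gp120 individually will be tested". A reader might infer that three of these four targets are vaccine-matched. That holds only if proteins A, B and AE are the vaccine proteins, which the section does not state. Results are tabulated by protein, and no rule ranks regimens on ADCC.

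These points narrow the problem. They do not remove the pooled definition or its conflict with the Protocol.

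**Conclusion.** The point holds for the aggregate score. SAP 10.2 gives two insert strains 29% of the weight in its neutralization AUC-MB and departs from the tier split that Protocol 6.4.4.3 requires. A T2 versus T3 difference in that score is therefore not, by itself, evidence of a heterologous difference.

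The counts and the 1.37-fold and 1.93-fold shifts are exact for detectable titers. The probabilities are illustrative: for a 3-fold matched-only gain, the test is positive anywhere from its nominal 5% up to 34% of the time, depending on assumed SDs and censoring. The Protocol's Tier 1B score is unaffected. Its Tier 2 score is affected, and wholly so only if "the tier 2 vaccine strains JR-FL and 92UG037.1" are the only tier 2 viruses run.

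**What to change.** In SAP 10.2:

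1. Restore the Protocol's separate Tier 1B and Tier 2 analyses and name the viruses in each panel.
2. Compute the magnitude-breadth curves and AUC-MB on heterologous viruses: the five tier 1B strains, and the heterologous tier 2 panel where it is run.
3. Report the vaccine-matched strains as a separate mean log titer, just as SAP 10.1 keeps the vaccine proteins apart from its breadth panels.
4. If JR-FL and 92UG037.1 are the only tier 2 viruses tested, still report that tier 2 result, label it vaccine-matched, and do not use it to rank regimens on breadth.

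Separating the GTL-ADCC targets in SAP 10.3 is an optional secondary display, worth adding only if gp120 A, B and AE are confirmed to be the vaccine proteins.

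The cost is wording and reprogramming, with no new assays. The main score uses five committed viruses instead of seven and is slightly noisier. Without the optional panel there is no heterologous tier 2 score, and the report should say so.

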10.5.3 Antibody-Dependent Cellular Cytotoxicity assay (ADCC) (Part B)

ADCC activity may be assessed using serum samples from study participants taken at the primary immunogenicity timepoints. Specimens from the baseline and other timepoints may also be analyzed at the discretion of the HVTN Laboratory Program, which may be contingent on the results of the primary immunogenicity timepoints. For the Granzyme B flow-based cytotoxicity assay, participant sera are incubated with effector cells and gp120-coated target cells. ADCC is quantified as net percent granzyme B activity which is the percent of target cells positive for GranToxiLux (GTL), an indicator of granzyme B uptake, minus the percent of target cells positive for GTL when incubated with effector cells but without sera. For the Luciferase-based cytotoxicity assay, participant sera are incubated with infectious molecular clone (IMC)-infected cells and percent killing is measured through the use of Vivirene luminescence.

10.6 Genotyping

Molecular human leukocyte antigen (HLA) typing may be performed on enrolled participants using cryopreserved PBMC collected at baseline, initially on specimens from participants who demonstrate vaccine-induced T-cell responses at postvaccination timepoints. Other participants (including control recipients) may

be HLA-typed to support future studies of immunological interest at the discretion of the HVTN Laboratory Program. Other markers, such as genes associated with immune responses or HIV-1 disease progression may also be assessed.

10.7 Lab assay algorithm

The Lab Assay Algorithm lists assays to characterize cellular, humoral, and innate immune responses as well as host genetics that may be conducted to determine endpoints in HVTN vaccine trials. The type of assay(s) employed will be dependent on the response obtained by the primary immunogenicity assays at relevant timepoints. Please note that the Lab Assay Algorithm will be updated periodically to include new assays.

10.8 Exploratory studies

Samples may be used for other testing and research related to furthering the understanding of HIV immunology or vaccines. In addition, cryopreserved samples may be used to perform additional assays to support standardization and validation of existing or newly developed methods.

10.8.1 B-cell ELISpot (Part B)

B-cell ELISpot assays may be conducted on PBMCs to enumerate B cells that secrete HIV-specific antibodies. The total number of B cells secreting IgG and/or IgA will be compared to the number of B cells secreting HIV-specific antibodies using Env proteins as antigens. Responses will be reported as the percentage of antigen-specific B cells among total antibody-secreting cells.

